#### Control group treatments

Subjects will receive 24 hours of one-on-one treatment from the same therapist ([name]) that performed the conventional therapy for the experimental group. The treatment sessions will be identical to the conventional therapy provided to the experimental group. The treatment schedule will parallel that given to the experimental group (1-hour sessions, 3 times/week).

#### Clinical evaluations

Clinical evaluations will be performed before training, after 12 hours of treatment, after 24 hours of treatment and again at the 6-month followup. All clinical testing will be performed by an Occupational or Physical Therapist (TBN), who has extensive experience in performing these tests. He/she will be blinded to the study design and unaware of the sequence or content of training that subjects receive. The Fugl-Meyer Test of Motor Function will be used to assess motor impairments at the shoulder, elbow, wrist and fingers (Fugl-Meyer 1975). The Fugl-Meyer test scores reflexes and the ability to perform several movements and tasks on a 3-point scale. The Fugl-Meyer was designed for the recovery patterns observed after stroke and is very responsive to change in severe and moderately impaired subjects, but is less responsive in mildly impaired subjects (van der Lee 2001). The Action Research Arm Test (ARAT) (Lang 2006) is an impairment level measurement tool that assesses the functional limitations of the upper extremities. It is one of the most frequently used primary endpoints in UE training trials in stroke. The assessment incorporates 19 items that are divided into four subscales: Grasp, Grip, Pinch, and Gross movement. Item scores are summed to form a subtest score, and then a full-scale score. The ARAT has established reliability, responsiveness and validity in stroke subjects (Platz 2005). The Motor Activity Log (MAL) will be used to assess use of the limb at home (Uswatte 2006). It is a structured interview during which respondents are asked to rate how they use their more-impaired arm for 28 ADL in the home over a specified period. The MAL is administered independently to the patient and an informant. Activities include brushing teeth, buttoning a shirt or blouse, and eating with a fork or spoon. For each item the participant must report how well (6-point, Quality of Movement or QOM scale) and how often (6-point, Amount of Use scale) each activity was performed during a specified period. The MAL has high internal consistency, test-retest reliability, and high convergent validity (Uswatte 2005).

### Secondary outcome variables

We will also perform the Box and Blocks test as a secondary measure of function. The Box and Blocks (Platz 2005) scores the number of one-inch blocks that can be moved from one box to another over a partition in one minute. We did not include Box and Blocks as a primary outcome because we are unaware of any studies that have estimated MCID for this test in chronic stroke. However, we include this as a secondary measure because of our pilot study results, which showed that conventional therapy was especially effective in affecting performance gains in this outcome if preceded by a period of robotic therapy.

To assess the movement strategies used by the upper limb, three dimensional motion analyses will be performed pre-treatment, post-treatment and at the 6-month followup. We will use a protocol for data collection currently being used as part of an ongoing VA Merit Review Project. We will measure the three dimensional movements of the arm and trunk during the performance of standardized versions of common everyday tasks. These tasks include placing a nut on a bolt, shelving boxes, taking a drink from a water bottle, opening a jar, etc. We will use an electromagnetic motion capture system, the MiniBirds® (Ascension Technologies) controlled by the Motion Monitor® Software (Innovative Sports Technology). The electromagnetic markers will be placed at the first thoracic vertebrae spinous process, acromion, the lateral aspect of the brachium, distal dorsal aspect of the antebrachium, dorsum of the hand at the base of the third metacarpal, thumb nail, index finger nail. These sensors will record body segment and finger movements in 3D space with a sampling rate of 120 Hz. The procedure for identifying landmarks and generating segment local coordinate frames is integrated into the Motion Monitor software. The output metrics will be grasp aperture and range of motion at the trunk, glenohumeral, elbow and wrist joints. After training, we expect less trunk movement, larger range of movement at the glenohumeral and elbow joints, and larger grasp aperture. Biomechanical data is not required to test the hypotheses of the study, but will be used in secondary analysis to further explore the changes in clinical scales observed in subjects.

### Data analysis

Prior to conducting the main analyses, summary statistics, histograms, and scatter plots will be inspected to verify that distribution assumptions are met. Adjustments (e.g., transformations) to the main dependent measures will be made as necessary to address any problems (e.g., skewness, outliers) that these preliminary analyses uncover. To test Hypotheses, a series of mixed model ANOVAs will be tested, one for each dependent variable, with the within-subject variable being timepoint (pre, after 12 hours of treatment, after 24 hours of treatment, 6 month followup) and the between-subject variable of group (experimental vs. control). A significant effect of timepoint or a significant timepoint x group interaction would be followed with a series of paired t-tests, with Bonferoni corrections. Hypothesis I will be tested with a paired t-test between the pre and post-robotic timepoint (after 12 hours of robotic treatment). Hypothesis II will be tested with a paired t-test between the pre and post-treatment timepoint in the experimental group (after 12 hours of robot and 12 hours of conventional therapy). Additionally a z-test will be performed for the hypothesis that the proportion of subjects with 10% or greater gain at the post-treatment timepoint is significantly greater than zero. A final paired t-test and z-test between pre and 6-month followup timepoints will be performed. If a change is statistically significant, mean changes will be compared to predetermined MCID values of 10% of full scale. To test Hypothesis III, the timepoint x group interaction effect will be examined in the mixed model ANOVA. If significant, gains in the dependent variables will be calculated at the post-treatment and 6-month timepoints (relative to the pre timepoint), and between-group differences will be tested with unpaired t-tests, with Bonferoni corrections.

In secondary analysis, we will look to identify the characteristics of patients who are most responsive to the treatment. Potential predictors include initial impairment level, and time-varying predictors such as amount of home use (MAL) at the previous assessment. The subjects will be divided into severe (Fugl-Meyer<30), moderate (30<Fugl-Meyer<50) and mild impairment groups (Fugl-Meyer>50). This division is based on a previous study that reported subjects with initially moderate impairment (Fugl-Meyer = 40) benefited the most from robotic therapy, with reduced effectiveness in severe and mildly impaired subjects (Hsieh 2012). The dependent variables will be gain in the FM, ARAT and MAL at each timepoint. A fixed effects (mixed) model will be used to determine if the gains over time were the same across the 3 impairment groups, and whether use at home in the preceding time interval predicts later improvement.

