## 3. Aims / Hypotheses

Specific AIM: We will perform a clinical trial to compare the effectiveness of robotic training to conventional therapy from an occupational therapist. To take advantage of the facilitatory effect of robot therapy on subsequent conventional therapy, the experimental treatment will be 12 hours of robot therapy followed by 12 hours of conventional therapy. Chronic stroke

subjects (N=46) will be randomly assigned to receive this experimental treatment or 24 hours of conventional therapy from an occupational therapist.

**Hypothesis I:** Gains from the initial 12 hours of robotic therapy will be significant ( $p < 0.05$ ) in the domains of impairment (Fugl-Meyer), function (Action Research Arm Test) and amount of arm use (Motor Activity Log).

**Hypothesis II:** Gains in impairment, function and arm use in the experimental group (robot + conventional therapy) will be significant ( $p < 0.05$ ) and clinically important (defined as greater than 10% gain) immediately after all treatments and also at the 6-month follow-up.

**Hypothesis III:** Gains in impairment, function and arm use will be significantly greater in the experimental group (robot + conventional therapy) than the conventional therapy control group immediately after the end of all treatments and also at the 6-month follow-up.

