### Power Analysis

The power analysis was based on data from our previous pilot study (Brokaw 2014). To address Hypothesis I, we calculated power to detect significant gains after only the robotic training. Using the pre-post changes after the initial period of robotic therapy from our pilot study, the effect size for the ARAT was  $d_z=1.2$ , with pre-post correlation  $r=0.94$ . In order to detect an effect this large, when using a 1-tailed paired t-test with  $\alpha=.05$ , a sample size of **N=8** is required for power > 0.90 (Faul 2009). For the Fugl-Meyer, the effect size was  $d_z=0.74$ , with pre-post correlation  $r=0.85$ , which would require a sample size of **N=18** for power > 0.90.

To power Hypothesis II, the pre-post effect size for gains on the ARAT after the experimental treatment (12 hours of robot + 12 hours of conventional therapy) was  $d_z=0.77$ , with pre-post correlation  $r=0.95$  (only using data from subjects who received robotic therapy followed by conventional therapy). In order to detect an effect this large, when using a 1-tailed paired t-test with  $\alpha=.05$ , a sample size of **N=16** is required for power > 0.90. For the Fugl-Meyer, the pre-post effect size was  $d_z=1.41$ , with pre-post correlation  $r=0.91$ . In order to detect this difference, only **N=6** subjects are required for power > 0.90.

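### If the paired tests for Hypotheses I and II are Bonferroni-corrected, Holm's procedure over the same three contrasts would add about 4 to 15 points of power on the weaker tests at the same familywise error

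*Combined protocol and SAP*

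**What the plan says.** The Data analysis section fits a mixed-model ANOVA to each outcome and sets the follow-up rule: "A significant effect of timepoint or a significant timepoint x group interaction would be followed with a series of paired t-tests, with Bonferoni corrections". The paired tests that answer the hypotheses come next:

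- The first, for Hypothesis I, compares the baseline visit with the visit that closes the robot sessions.
- The second is given as: "Hypothesis II will be tested with a paired t-test between the pre and post-treatment timepoint in the experimental group"
- The third is given as: "A final paired t-test and z-test between pre and 6-month followup timepoints will be performed"

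None of these three sentences repeats the correction, whereas the Hypothesis III sentence on unpaired tests does. The section does not say how many tests share the correction, whether the family covers one outcome or all three, or whether the tests are one- or two-sided. The Power Analysis section uses a "1-tailed paired t-test with" an alpha of 0.05 for Hypotheses I and II, with no adjustment, and a target power above 0.90.

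**The concern.** Bonferroni over three contrasts tests each at 0.05/3, however strong the other two are. Holm also starts at 0.05/3, but after each rejection it relaxes the threshold to 0.05/2 and then to 0.05. It controls the familywise error under any dependence and rejects everything that Bonferroni rejects.

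The plan's effect sizes are of the kind where this matters, because each outcome pairs a near-certain contrast with a weaker one. Fugl-Meyer has a standardised paired effect (dz) of 1.41 at 24 hours and 0.74 at 12 hours. ARAT has 1.2 at 12 hours and 0.77 at 24 hours. With 19 completers in the arm, the power given up on the weaker contrasts is worth recovering. Hypothesis II also asks for significance at both 24 hours and 6 months, so the loss falls on a joint requirement.

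**Working it through.** **Inputs.** From Power Analysis: dz = 0.74 (Fugl-Meyer, 12 hours), 1.41 (Fugl-Meyer, 24 hours), 1.2 (ARAT, 12 hours), 0.77 (ARAT, 24 hours); 19 completers per group. From Aims / Hypotheses: alpha 0.05. Assumed, because the documents give neither: the 6-month dz, and a correlation of 0.5 to 0.7 between the gains at different visits.

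**Step 1: the plan's own figures.** Paired t-test power comes from the noncentral t with n − 1 degrees of freedom and noncentrality dz·√n. At one-sided 0.05 the stated sample sizes of 8, 18, 16 and 6 give power of 0.919, 0.914, 0.902 and 0.903. All four reproduce, without any multiplicity adjustment.

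**Step 2: power at n = 19, by threshold.** The noncentralities are 0.74 × √19 = 3.226 and 0.77 × √19 = 3.356, with 18 degrees of freedom.

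| Contrast | Sidedness | 0.05/3 | 0.05/2 | 0.05 |
|---|---|---|---|---|
| Fugl-Meyer, 12 hours | one | 0.813 | 0.862 | 0.927 |
| ARAT, 24 hours | one | 0.844 | 0.887 | 0.943 |
| Fugl-Meyer, 12 hours | two | 0.716 | 0.775 | 0.862 |
| ARAT, 24 hours | two | 0.755 | 0.810 | 0.887 |

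The 0.05/3 column is Bonferroni over the three contrasts. The 0.05 column is the most that Holm can reach.

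**Step 3: Holm with no 6-month effect.** The strong contrast is rejected almost always, so the weaker one is tested at about 0.05/2. The gain is roughly the second column minus the first:

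- one-sided: 0.862 − 0.813 = 0.049 and 0.887 − 0.844 = 0.043
- two-sided: 0.775 − 0.716 = 0.059 and 0.810 − 0.755 = 0.055

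That is about 4 to 6 points.

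**Step 4: Holm with a 6-month effect.** I simulated experimental arms of 19 with correlated gains and let the 6-month dz run from 0.5 up to the 24-hour value (1.41 for Fugl-Meyer, 0.77 for ARAT).

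| Contrast | Sidedness | Bonferroni | Holm |
|---|---|---|---|
| Fugl-Meyer, 12 hours | one | 0.81 | 0.87–0.93 |
| ARAT, 24 hours | one | 0.84 | 0.89–0.93 |
| Fugl-Meyer, 12 hours | two | 0.72 | 0.79–0.86 |
| ARAT, 24 hours | two | 0.755 | 0.82–0.86 |

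The gains are about 5 to 11 points one-sided and 6 to 15 two-sided. The contrasts with dz 1.2 and 1.41 gain under 1 point. For all three Fugl-Meyer contrasts together (two-sided, 6-month dz 0.74), power rises from 0.57–0.60 to 0.76–0.78.

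**Step 5: error control.** Simulated one-sided familywise error of Holm over three contrasts, at correlations 0, 0.5 and 0.8, was 0.035 to 0.049 with no true effect and 0.039 to 0.050 with one true effect (dz 1.2).

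These figures do not model the ANOVA condition that precedes the paired tests.

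**The case against.** **The correction may not apply to these tests.** It is attached to the general follow-up series. The sentences for Hypotheses I and II omit it, the Hypothesis III sentence repeats it, and the sample sizes were computed without it. If the sponsor means these tests to be uncorrected, their one-sided power is already 0.93 and 0.94, and adopting Holm would lower it or at best leave it about the same. This objection stands as a limit: the gain exists only on the natural reading, and the text leaves the other open.

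**Sidedness.** The gain holds only when the two methods are compared at the same sidedness. Moving from one-sided Bonferroni to two-sided Holm would change Fugl-Meyer from 0.81 to 0.79–0.86 and ARAT from 0.84 to 0.82–0.86, so power could fall. The fix must therefore leave sidedness alone.

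**The size rests on an unseen effect.** The upper end of the range needs the Fugl-Meyer gain to be fully or almost fully retained at 6 months, with two-sided testing. This also stands, which is why the range reaches down to 4 points.

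**Bonferroni is valid and has simple matching confidence intervals.** This is true. A reader might infer that the planned analysis is wrong or inflates false positives. The documents do not support that: plain Bonferroni controls the error, conservatively. Nor do they support a reading that the trial as a whole is underpowered because of this choice. The between-group tests of Hypothesis III are not touched.

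**Conclusion.** The point holds as a cheap improvement. On the natural reading of the Data analysis section, Bonferroni over the three contrasts takes the two weaker tests from unadjusted one-sided power of 0.93 and 0.94 to 0.81 and 0.84, below the plan's own target of 0.90. Holm recovers part or most of that at no cost in familywise error. One-sided power returns above 0.90 if the 6-month effect stays near the 24-hour effect, but not for every 6-month effect considered.

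The conclusion depends on four things: that the three named contrasts are the corrected series, with one family per outcome; 19 completers; the pilot effect sizes; and an assumed 6-month effect and correlation. Only the size depends on the last of these. The direction does not, because Holm never rejects less than Bonferroni over the same family.

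**What to change.** Keep the ANOVA condition and the plan's chosen sidedness, and change only the correction for the paired tests:

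> For each outcome, the three paired contrasts in the experimental group (pre vs 12 hours, pre vs 24 hours, pre vs 6 months) form the confirmatory family and are tested with Holm's step-down procedure at familywise 0.05; any other paired visit comparisons are exploratory.

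State the sidedness once in Data analysis so that it agrees with Power Analysis. If the sponsor instead intends the Hypothesis I and II tests to be uncorrected, the section should say so.

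The cost is one sentence and no extra patients. The small downside is that simultaneous confidence intervals matching Holm are less simple than Bonferroni intervals. If unadjusted 95% intervals are shown beside Holm-adjusted p-values, the report should say that the two can disagree.

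### The z-test that the responder proportion exceeds zero has a degenerate null, so it cannot support the clinical-importance part of Hypothesis II, and the plan does not say whether it or the mean-versus-MCID check governs

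*Combined protocol and SAP*

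**What the plan says.** Section 3 (Aims / Hypotheses) requires the experimental-arm gains in Hypothesis II to be statistically significant and also "clinically important (defined as greater than 10% gain) immediately after all treatments and also at the 6-month follow-up". Section 5, Data analysis, gives three procedures for this:

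- Significance: "Hypothesis II will be tested with a paired t-test between the pre and post-treatment timepoint in the experimental group".
- A responder test, by z-test, of whether "the proportion of subjects with 10% or greater gain at the post-treatment timepoint is significantly greater than zero". It is repeated later: "A final paired t-test and z-test between pre and 6-month followup timepoints will be performed".
- A comparison of means: "If a change is statistically significant, mean changes will be compared to predetermined MCID values of 10% of full scale".

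The plan gives no other reference proportion for the z-test, no variance formula and no sidedness. It plans no comparison of responder proportions with the control arm. It does not say whether the responder test or the comparison of means decides clinical importance.

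**The concern.** A responder proportion of exactly zero is not a meaningful null. Measurement error and day-to-day variation alone will carry some patients past 10% of full scale, so rejecting zero shows only that at least one patient crossed the line. Yet this is the only formal test attached to the clinical-importance half of Hypothesis II. The other criterion sets a point estimate against the MCID with no statement of uncertainty. With two criteria of very different strictness and no rule of precedence, the claim could rest on whichever is met, for three outcomes at two timepoints.

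**Working it through.** **The plan's own figure.** The Power Analysis gives sample sizes for Hypothesis II only for the paired t-test. With power = P(noncentral t on n−1 df, noncentrality d_z√n, exceeds t at 0.95), d_z = 0.77 gives n = 16 (power 0.902) and d_z = 1.41 gives n = 6 (power 0.903). Both reproduce. There is no power or error rate for the z-test to reproduce.

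**Inputs.**
- Thresholds of 10% of full scale (Background): 6.6 points Fugl-Meyer, 5.7 ARAT.
- Gains after the experimental treatment (Power Analysis): Fugl-Meyer 7 (SD 4.9), ARAT 5.6 (SD 4.7).
- Gains after conventional therapy, from cited studies (Power Analysis): Fugl-Meyer 2.47 (SD 1.67), ARAT 1.0 (SD 5.7).
- Completers per arm: 19.
- Assumption: gains are normally distributed.

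**1. The null.** SE₀ = √(p₀(1−p₀)/n) = √(0 × 1/19) = 0. The statistic is undefined, and one responder is impossible under the null.

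**2. The usual workaround.** Take the SE from the observed proportion (Wald): z = p̂/√(p̂(1−p̂)/19). Two responders give 1.50, three give 1.89, four give 2.25. So three of 19 pass one-sided (1.645) and four of 19 pass two-sided (1.960).

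**3. How often the z-test alone passes.** Responder probability p = 1 − Φ((threshold − mean)/SD); the passing rates are binomial tails with n = 19.

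| Outcome, mean gain, SD | p | ≥1 of 19 | ≥3 of 19 | ≥4 of 19 |
|---|---|---|---|---|
| Fugl-Meyer, 0, 4.9 | 8.9% | 83% | 24% | 8% |
| ARAT, 0, 4.7 | 11.3% | 90% | 36% | 16% |
| ARAT, 0, 5.7 | 15.9% | 96% | 60% | 36% |
| Fugl-Meyer, 0, 1.67 | 0.004% | 0.1% | ≈0 | ≈0 |
| Fugl-Meyer, 2.47, 1.67 (conventional) | 0.7% | 12% | 0.03% | ≈0 |
| ARAT, 1.0, 5.7 (conventional) | 20.5% | 99% | 78% | 57% |

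**4. Joint rule at zero gain** (200,000 simulated trials, n = 19). For Fugl-Meyer with SD 4.9, a significant one-sided t-test plus at least one responder occurs in 4.9%, and plus at least three in 3.1%. With a two-sided t-test and at least one responder it is about 2.4%. For ARAT with SD 5.7 the one-sided figures are about 5.0% and 4.8%. A significant t-test with an observed mean at or above the MCID is essentially never seen.

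**5. Joint rule at a real gain below the MCID.** Assume a true gain of half the MCID.
- Fugl-Meyer 3.3 (SD 4.9): one-sided t-test plus at least one responder passes 88%, plus at least three 81%. The observed mean reaches 6.6 with probability 1 − Φ(3.3/(4.9/√19)) = 1 − Φ(2.94) = 0.2%.
- ARAT 2.85 (SD 4.7): 81% and 78%. The observed mean reaches 5.7 with probability 1 − Φ(2.85/(4.7/√19)) = 1 − Φ(2.64) = 0.4%.
- Fugl-Meyer 2.47 with SD 4.9 (a mix of the two sources, also an assumption): 68% and 58%, against about 0.01–0.02% for the mean.

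The two criteria would therefore routinely disagree in exactly the range where the label matters.

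**The case against.** A reader might infer that Hypothesis II is unfalsifiable, or that an ineffective treatment would be declared clinically important. The documents do not support that. Section 3 requires gains that are both significant and clinically important, and the z-test comes in addition to a paired t-test, which alone holds joint false confirmation at zero gain to about 5% one-sided or 2.5% two-sided. The 83–96% describes the z-test by itself. The plan also compares the mean change with the MCID, and a treatment with no effect would almost never pass that.

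The size is also sensitive to the inputs. Three of 19 suffices only one-sided, and the plan states one-tailed testing for its t-tests, not for the z-test. At the cited conventional-therapy Fugl-Meyer figures the chance of any responder is only 12%. The pilot SD of 4.9 may include real differences in response as well as noise. Finally, Hypothesis II is deliberately within-group; the randomised comparison belongs to Hypothesis III.

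All of this limits the consequence. None of it rescues the test, since no choice of SD or sidedness makes a zero null informative about clinical importance. Nor does the mean-versus-MCID check settle the matter, because the plan does not say that it prevails.

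**Conclusion.** The point holds in a limited form. The z-test against zero is invalid as written at both timepoints and cannot carry the clinical-importance claim. At zero mean gain with SDs of 4.7 to 5.7 it passes 83–96% (any responder), 24–60% (one-sided Wald) or 8–36% (two-sided Wald), and close to 0 for Fugl-Meyer with SD 1.67. False confirmation of the whole hypothesis at zero gain stays near 5%. The exposure lies with gains that are real but below the MCID: at half the MCID, one-sided t-test plus z-test passes about 78–88%, against under 0.5% for the mean reaching the MCID.

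This rests on normal gains, 19 completers and reading a 10% gain as 10% of full scale, as the Background and the mean comparison do. If it meant 10% of a baseline near 21, about 33% would respond at zero gain and even the four-responder version would pass at least 91% of the time. Nothing can be computed for the Motor Activity Log, for which the documents give no data.

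**What to change.** - Delete the z-test against zero at post-treatment and at 6 months.
- Define a responder as a gain of at least 10% of full scale (6.6 Fugl-Meyer, 5.7 ARAT), and state the point value for the Motor Activity Log. Compare the proportions between the randomised arms with an exact test and a confidence interval for the difference. Report the experimental-arm proportion with an exact confidence interval.
- Report the mean gain with its 95% confidence interval beside the MCID, and state that the mean-versus-MCID comparison decides the within-group statement.
- Do not require the lower confidence limit to reach the MCID. At the plan's expected Fugl-Meyer effect the limit would be about 7 − 2.101 × 4.9/√19 = 4.6, against 6.6. Such a rule would succeed only about 5% of the time for Fugl-Meyer and 2% for ARAT.

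**Cost.** Only analysis wording changes; the assessments are already scheduled in both arms. The between-arm comparison is a new analysis with modest power. At the plan's ARAT figures the proportions would be 49% and 20%, and Fisher's exact test with 19 per arm has about 49% power one-sided or 36% two-sided. The clinical-importance claim becomes harder to make.

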### **Recruitment**

Subjects will be recruited from the outpatient clinics at the Washington DC VAMC. The DC VAMC annually has over 100 admissions for stroke. [name], has WOC status at the DC VAMC and will confirm that patients meet study criteria. Additionally, veterans will be recruited from nearby MedStar National Rehabilitation Hospital (NRH), Washington Hospital Center (WHC), and Medstar Health outpatient clinics.

The inclusion criteria are: 1) Age 21 or older; 2) ischemic or hemorrhagic stroke (with confirmatory neuroimaging) that occurred more than 6 months before entering the study; 3) presence of voluntary hand activity indicated by a score of at least 1 on the finger mass extension/grasp release item of the Fugl-Meyer Test of Motor Function; 4) adequate cognitive status, as determined by Mini-Mental Status Examination (Bleeker 1988) score >24; 5) no upper extremity injury or conditions that limited use prior to the stroke. Subjects will be excluded if they: 1) cannot give informed consent; 2) have clinically significant fluctuations in mental status within a month of enrollment; 3) were not independent prior to the stroke as measured by scores <95 on the Barthel Index (de Morton 2008) or >1 on the Modified Rankin Scale (Quinn 2009); 4) have hemispatial neglect as determined by >3 errors on the Star Cancellation Test (Manly 2009); 5) have severe sensory loss as determined by a score of 2 on the sensory item of the NIHSS (Lai 1988); 6) receiving oral or injected antispasticity medications during study treatment; 7) pain that interferes with daily activities; 8) history of prior stroke.

In a previous study in chronic stroke, we found that the dropout rate was 16.7%, so we will plan to **recruit 46 subjects**. Subjects who drop out of the study will be replaced until a total of **38 subjects complete the protocols**. All therapy will be in addition to the regular PT and OT subjects may be receiving as part of their outpatient treatment. The amount of outside PT or OT targeting arm or hand function received by subjects while enrolled in the study will be logged and used as a potential covariate in the analysis.

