To address Hypothesis III, we calculated the power to detect the expected differences in gains between the experimental and control groups. The experimental treatment in our pilot study produced gains of 7 (sd=4.9) in the Fugl-Meyer. A recent study reported gains of 2.47 (sd=1.67) on the Fugl-Meyer after 24 hours of conventional therapy in 35 stroke subjects with similar intake Fugl-Meyer scores as in our pilot study (FM = 22.4 vs. 21) (Klamroth-Marganska 2014). Using these data, the mean difference in treatments will have an effect size of 1.9. For a 1-tailed unpaired t-test, **N=5** subjects in each treatment group are needed to detect this difference with power > 0.80. Similarly for the ARAT, we had gains of 5.6 (sd=4.7) after the experimental treatment in our pilot study. A different study (Fleming 2015) reported gains of 1.0 (sd=5.7) after 24 hours of conventional therapy in 17 chronic stroke subjects with similar intake ARAT scores as in our pilot study (ARAT = 26.6 vs. 20.9). Using these data, the mean difference in treatments will have an effect size of 0.84. For a 1-tailed unpaired t-test, **N=19** subjects in each treatment group will detect this difference with power > 0.80.

Therefore with **N=19** subjects in each treatment group, we will detect the anticipated pre-post changes and group differences in the ARAT and Fugl-Meyer. We had a dropout rate of 0.167 in the pilot study. Therefore, we will plan for this and recruit 23 subjects into each treatment group. We have no pilot data on the MAL to perform a power analysis for the outcome.

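### Hypothesis III's two group contrasts sit behind a 3-df interaction test that the sample size ignores; test them directly, adjusted for baseline, and keep outside therapy out of the model

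*Combined protocol and SAP*

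**What the plan says.** Hypothesis III (Aims / Hypotheses) expects larger gains in the experimental group at the end of all treatment and at 6 months. It makes no between-group claim at the 12-hour visit.

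The Data analysis section starts from an omnibus test: "To test Hypothesis III, the timepoint x group interaction effect will be examined in the mixed model ANOVA". The within-subject factor has four levels (pre, 12 hours, 24 hours, 6 months) and there are two groups, so the interaction has (4 − 1)(2 − 1) = 3 df. The next step is conditional: "If significant, gains in the dependent variables will be calculated at the post-treatment and 6-month timepoints (relative to the pre timepoint), and between-group differences" go to unpaired t-tests with Bonferroni correction. The section does not give the number of tests corrected for or the sidedness. No baseline score or other covariate is named for this comparison.

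The Power Analysis rests on a single test: "For a 1-tailed unpaired t-test, N=19 subjects in each treatment group will detect this difference with power > 0.80".

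The Recruitment section says that physical or occupational therapy for the arm or hand obtained outside the study during enrolment "will be logged and used as a potential covariate in the analysis". It does not say which analysis, or what would decide its inclusion.

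**The concern.** Three features of the Hypothesis III comparison need attention.

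- **The gate does not match the hypothesis.** The F-test spreads its power over every pattern of group difference across four visits, including the 12-hour visit. If it misses, the two contrasts of interest are never tested, however large the 24-hour difference. A Bonferroni penalty follows if it passes. The stated power of more than 0.80 describes neither step.
- **The baseline score is collected but unused in the comparison.** The protocol itself expects gains to depend on starting level: Clinical evaluations notes weaker Fugl-Meyer responsiveness in mild impairment, and the secondary analysis splits subjects by initial Fugl-Meyer. With 19 per arm and no stratification described, a chance imbalance could show up in the gains.
- **Outside therapy accrues after randomisation.** If assignment or progress affects how much a subject seeks, conditioning on it can distort the treatment contrast. Calling it a potential covariate leaves that choice open until the data are seen.

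At stake is a real end-of-treatment difference going untested, and a stated power that the planned procedure does not deliver.

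**Working it through.** **Inputs.** From the Power Analysis: ARAT gains 5.6 (SD 4.7) and 1.0 (SD 5.7, n = 17); d = 0.84; 19 per arm; one-tailed; pre-post correlations 0.85 to 0.95. Alpha 0.05 is stated for the paired tests and assumed here for Hypothesis III. Bonferroni is assumed to cover two timepoints (0.025 each).

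**Step 1: reproduce the plan's figure.** Assuming 6 pilot subjects had the experimental sequence (half of the 12 randomised), the pooled SD is √[(5 × 4.7² + 16 × 5.7²)/21] = 5.48, and d = (5.6 − 1.0)/5.48 = 0.84. Power follows from a noncentral t on 2n − 2 = 36 df with noncentrality d√(n/2) = 0.84 × √9.5 = 2.59. At one-sided 0.05 it is 0.815, and 19 is the smallest n reaching 0.80. The figure reproduces.

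**Step 2: add Bonferroni, no gate.** The same formula at 0.025 gives 0.712 one-sided and 0.601 two-sided. Reaching 0.80 would take 24 or 29 per arm respectively.

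**Step 3: add the gate.** I simulated 20,000 trials per profile, with 19 per arm, compound symmetry, r = 0.95 and complete data. The interaction F was tested at 0.05, followed by the t-test on the 24-hour gain. Profiles give the group difference at pre, 12 h, 24 h and 6 months as multiples of 0.84 gain-SDs. The documents give no such profiles; these are assumptions.

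| Profile | F significant | Gated, one-sided 0.05 | Gated, one-sided 0.025 | Gated, two-sided 0.025 |
|---|---|---|---|---|
| 0, 0, 1, 1 | 0.87 | 0.76 | 0.68 | 0.59 |
| 0, ½, 1, 1 | 0.70 | 0.66 | 0.62 | 0.56 |
| 0, 1, 1, 1 | 0.75 | 0.69 | 0.64 | 0.57 |
| 0, ½, 1, ½ | 0.55 | 0.55 | 0.53 | 0.51 |
| 0, ½, 1, 0 | 0.71 | 0.66 | 0.62 | 0.56 |
| No gate | – | 0.81 | 0.71 | 0.60 |

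Repeat runs move these by up to about 0.01. Each column compares like with like:

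- one-sided 0.05: the gate costs 5 to 27 points;
- one-sided 0.025: 3 to 18 points;
- two-sided 0.025: 1 to 9 points.

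**Step 4: baseline adjustment.** With equal SDs at both visits, the variance of the adjusted contrast relative to the gain score is (1 + r)/2, so the saving is (1 − r)/2. Power uses 2n − 3 = 35 df and a small-sample covariate penalty of 1 + 1/(2n − 4).

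| r | Variance saved | One-sided 0.05 | Two-sided 0.025 |
|---|---|---|---|
| Unadjusted gain | – | 0.815 | 0.601 |
| 0.95 | 2.5% | 0.813 | 0.599 |
| 0.91 | 4.5% | 0.820 | 0.609 |
| 0.85 | 7.5% | 0.831 | 0.624 |
| 0.70 (assumed) | 15% | 0.857 | 0.665 |
| 0.50 (assumed) | 25% | 0.893 | 0.725 |

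Over the plan's range the change is −0.2 to +2.3 points. The last two rows show what a lower 6-month correlation would do; the documents give none.

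**Step 5: outside therapy.** Set side by side, the Data analysis section puts only timepoint and group in the Hypothesis III model, while the Recruitment section leaves a post-randomisation covariate open for an unnamed analysis. No arithmetic applies.

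**The case against.** An omnibus interaction followed by corrected contrasts is conventional, pre-specified and conservative. At two-sided 0.025 the gate's cost can be as little as one point. That is fair, but the gate is not needed for error control: Bonferroni over two timepoints already holds the family-wise error for each outcome to at most 0.05. The gate adds a loss of power and ties the result to a visit that Hypothesis III does not name.

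Four stronger readings are tempting, and the documents do not support them.

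- *The gate takes power from 0.71 to 0.51–0.59.* Setting two-sided gated power at 0.025 against an ungated two-sided 0.05 test (0.712) also removes Bonferroni. That correction accounts for 0.712 − 0.601 = 11 points and is legitimate with two timepoints.
- *High pre-post correlations make baseline adjustment powerful.* The reverse holds. With r near 1, the gain score has already removed nearly all between-subject variance.
- *Unadjusted gains are biased.* Under randomisation with complete data they are not. Chance imbalance is sampling variation and is already in the standard error.
- *The plan adjusts Hypothesis III for outside therapy, its only covariate.* The Data analysis section does not put it there, and nothing shows that the arms will differ in it. The secondary analysis also names initial impairment, a baseline variable, as a predictor.

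**Conclusion.** The point holds for the gate, and in a limited way for the covariates. The Hypothesis III contrasts depend on a 3-df test that does not target them, and the sample size covers neither that test nor the Bonferroni correction. As planned, power for the 24-hour ARAT contrast is about 0.53–0.68 one-sided or 0.51–0.59 two-sided, against a stated figure above 0.80. Part of that shortfall is the gate and part is the correction.

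Baseline adjustment is worth having as protection against chance imbalance, and for a possible gain if the 6-month correlation is lower. It does little for power at r = 0.85 to 0.95. The outside-therapy risk is conditional on its being used in the treatment comparison.

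These sizes rest on compound symmetry, equal SDs, complete data, assumed time profiles and two tests in the Bonferroni family. With six tests, ungated power would be 0.537 one-sided or 0.431 two-sided. They also take d = 0.84 at face value. Its input, "we had gains of 5.6 (sd=4.7) after the experimental treatment in our pilot study", is given in the Background as the gain after the first robot period only. Its ratio 5.6/4.7 = 1.19 also differs from the d_z of 0.77 stated for the full experimental treatment. Those places must be reconciled.

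**What to change.** 1. Drop the interaction test as a condition for Hypothesis III. Fit one repeated-measures model per outcome to the 12-hour, 24-hour and 6-month scores, with group, timepoint, group-by-timepoint, baseline score and baseline-by-timepoint as fixed effects. State the covariance structure.
2. Test Hypothesis III by the group contrasts at 24 hours and 6 months from that model. Keep Bonferroni across the two timepoints (0.025 each), state the sidedness, and say whether the correction extends across outcomes.
3. Restate the Power Analysis under that rule: about 0.71 one-sided or 0.60 two-sided for the ARAT at 19 per arm.
4. Keep outside therapy out of the treatment-comparison model and tabulate it by arm.

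The cost is a wording change, slightly more analysis work and a less favourable stated power. No additional data or visits are needed.
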